10.4.2 Recording, Assessing Causality, and Follow-up of Complaints, PQCs/Malfunctions

Malfunction which may lead to SAEs will be reported to the Sponsor within 5 calendar days of the information via a paper reporting form.

10.7.2 EEA-specific Requirements

Section 5.2 Exclusion Criteria

For study sites in EEA countries, Exclusion Criteria 17 and 18 are as follows:

17. Received immunosuppressive therapy within 6 months before vaccination, including chemotherapeutic agents or other immunotherapies/immunomodulators used to treat cancer or other conditions, and interventions associated with organ or bone marrow transplantation, or autoimmune disease.

18. *Received any nonlive vaccine ≤ 15 days before receipt of study vaccine or is scheduled to receive any nonlive vaccine ≤ 30 days after receipt of any study vaccine. **Exception:** inactivated influenza vaccine and SARS-CoV-2 mRNA or protein subunit vaccine may be administered but must be given ≥ 15 days before or after receipt of study vaccine.

Section 10.2 Clinical Laboratory Tests

For study sites in EEA countries, the following note applies to [Table 8](#) (Blood Volumes Collected by Visit for Immunogenicity Assessments):

***NOTE:** This table specifies the maximum blood volume to be collected for each visit. The blood draw limit should not exceed the EMA recommendation of 0.9 mL/kg body weight, which corresponds to 1% of total blood volume at a single time point. Additionally, during a period of 4 weeks, the blood draw limit should not exceed 2.4 mL/kg body weight, which is equivalent to 3% of the total blood volume.*

Section 10.5.2 Contraceptive Requirements

For study sites in EEA countries, the contraceptive methods allowed during the study include only those methods considered to be highly effective, as specified below:

Contraceptives allowed during the study include:

Highly Effective Contraceptive Methods That Have Low User Dependency^a Failure rate of <1% per year when used consistently and correctly.

 • Progestogen-only contraceptive implant^{b,c} • IUS^{b,d} • Nonhormonal IUD • Bilateral tubal occlusion (Tubal occlusion includes tubal ligation)

 • Azoospermic partner (vasectomized or secondary to medical cause, confirmed by medical history) – All sexual partner(s) of the POCBP must be azoospermic. The participant must provide verbal confirmation of partner azoospermia during Medical History. If not, an additional highly effective method of contraception should be used. A spermatogenesis cycle is approximately 90 days.

Highly Effective Contraceptive Methods That Are User Dependent^a Failure rate of <1% per year when used consistently and correctly.

 • Combined (estrogen- and progestogen-containing) hormonal contraception^{b,c} 
 - Oral - Intravaginal - Transdermal - Injectable

 • Progestogen-only hormonal contraception^{b,c} 
 - Oral - Injectable

Sexual Abstinence
 
 • Sexual abstinence is considered a highly effective method only if defined as refraining from penile-vaginal intercourse with a partner capable of producing sperm, during the entire period of risk associated with the study intervention. The reliability of sexual abstinence needs to be evaluated in relation to the duration of the study and the preferred and usual lifestyle of the participant.

^a Typical use failure rates are higher than perfect-use failure rates (ie, when used consistently and correctly)
 
^b Penile/external condoms must be used in addition to the POCBP's hormonal contraception
 
^c If locally required, in accordance with CTFG guidelines, acceptable contraceptives are limited to those which inhibit ovulation
 
^d IUS is a progestin releasing IUD
 
Note: The following are not acceptable methods of contraception:
 
 • Periodic abstinence (calendar, symptothermal, postovulation methods), withdrawal (coitus interruptus), spermicides only, and LAM • Penile/external and vaginal/internal condom should not be used together (due to risk of failure with friction)

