1.3 Schedule of Activities

Study Period:	Intervention and Follow-up					Notes
Visit Number:	1	2	3	4	5	
Visit Type:	Visit	TC	Visit	TC	TC	
Study Day:	Day 1	Day 7	Day 30	Day 90	Day 180	
Visit Window:	-	Day 7 to Day 10	Day 30 to Day 44	Day 76 to Day 104	Day 166 to Day 194	
Administrative Procedures						
Screening Procedures						
Informed Consent/Assent	X					Must be obtained before any study procedures are conducted.
Informed Consent/Assent for Optional FBR	X					Must be obtained before FBR sample collection.
Assignment of Screening Number	X					
Participant Identification Card	X					
Inclusion/Exclusion Criteria	X					
Medical History	X					
Postrandomization Procedures						
Assignment of Randomization Number	X					
Prior/Concomitant Medication and Nonstudy Vaccination Review	X	X	X	X	X	
V116/PPSV23 Administration (blinded)	X					
Provide Electronic Device (if needed) or Configure Device (Personal or Provisioned) for eVRC Data Collection	X					Instructions for using the eVRC will be reviewed with the participant or participant's legally acceptable representative.
Review eVRC Data With Participant or Participant's LAR		X	X			
Collect Electronic Device From Participant or Participant's Legally Acceptable Representatives Who Received an Electronic Device or Deactivate Personal Devices			X			
Complete Telephone Contact Questionnaire				X	X	
Safety Procedures						
Complete Physical Examination	X					Performed by investigator or medically qualified designee before vaccination.
Pregnancy Test (if applicable)	X					Participants of childbearing potential must have a negative urine or serum test (consistent with local requirements and sensitive to ≤ 25 IU hCG) result before vaccination.

Study Period:	Intervention and Follow-up					Notes
Visit Number:	1	2	3	4	5	
Visit Type:	Visit	TC	Visit	TC	TC	
Study Day:	Day 1	Day 7	Day 30	Day 90	Day 180	
Visit Window:	-	Day 7 to Day 10	Day 30 to Day 44	Day 76 to Day 104	Day 166 to Day 194	
Body Temperature Measurement	X					Measured before vaccination. Participants with febrile illness (temperature $\geq 100.4^{\circ}\text{F}$ [$\geq 38.0^{\circ}\text{C}$]) within 72 hours before vaccination must be rescheduled.
Postvaccination Observation Period	X					Observed by blinded study-site personnel for at least 30 minutes postvaccination.
AE Monitoring	X	X	X	X	X	Nonserious AEs collected through Day 30 postvaccination; all SAEs and deaths collected through Day 180.
Immunogenicity Assessments						

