4 STUDY DESIGN

4.1 Overall Design

This is a Phase 3, randomized, double-blind, active comparator-controlled clinical study to evaluate the safety, tolerability, and immunogenicity of V116 in children and adolescents aged ≥ 2 to < 18 years who have completed a primary pneumococcal vaccination regimen and who are at increased risk of pneumococcal disease (ie, chronic heart disease, chronic lung disease, diabetes mellitus, chronic liver disease, or chronic kidney disease).

Approximately 820 participants will be randomized in a 3:2 ratio to receive a single dose of either V116 or PPSV23 on Day 1. Randomization will be stratified by the number of increased-risk conditions for pneumococcal disease (1 increased-risk condition, or ≥ 2 increased-risk conditions) and by prior pneumococcal vaccination and age:

- Prior PCV7 alone
- Prior PCV7 and one prior PPSV23 dose
- Prior PCV10 alone and ≥ 2 to < 6 years old
- Prior PCV10 alone and ≥ 6 to < 18 years old
- Prior PCV10 and one prior PPSV23 dose
- Prior PCV13 alone and ≥ 2 to < 6 years old
- Prior PCV13 alone and ≥ 6 to < 18 years old
- Prior PCV13 and one prior PPSV23 dose

Note: Participants who previously received a combination of PCV7, PCV10, and/or PCV13 or any doses of PCV15 or PCV20 will be excluded from this study.

Participants are to have ≥ 1 increased-risk condition listed in Inclusion Criteria #1 (Section 5.1). It is expected that ≥ 25 participants per risk condition will be enrolled. In participants with ≥ 2 increased-risk conditions, each condition will count towards the total per condition.

Participants risk condition(s) must be considered stable for ≥ 3 months with no anticipated major change in treatment expected for the duration of the study and with ≤ 1 hospitalization directly related to the risk condition within 3 months before study vaccination.

An eVRC will be used by the participant/participant's legally authorized representative to record solicited injection-site AEs, solicited systemic AEs, and daily body temperatures from Day 1 through Day 5 after vaccination. Unsolicited AEs will also be recorded from Day 1 through Day 30 after vaccination. The participant/participant's legally authorized representative will be provided an electronic device or have their own electronic device configured, if compatible, to complete the eVRC.

Blood samples for immunogenicity assays will be drawn on Day 1 (Visit 1) and Day 30 (Visit 3).

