5.1 Inclusion Criteria

An individual is eligible for inclusion in the study if the individual meets all of the following criteria:

Type of Participant and Disease Characteristics

1. Documented diagnosis of ≥ 1 of the following risk conditions for pneumococcal disease as determined by the investigator, according to local clinical standards, which includes history and physical examination in combination with diagnostic tests and procedures and managed per local guidelines:
 - Diabetes mellitus receiving treatment with antidiabetic medication
 - Chronic compensated liver disease
 - Chronic lung disease, including but not limited to asthma (a diagnosis of asthma requires current medical therapy)
 - Chronic heart disease due to heart failure, congenital heart disease, cardiomyopathy, and/or valvular heart disease
 - Chronic kidney disease, with chronic kidney insufficiency/impairment
2. Receiving stable medical management for the risk conditions listed in Inclusion Criterion #1 for ≥ 3 months with no anticipated major change in treatment expected for the duration of the study and with ≤ 1 hospitalization directly related to the risk condition within 3 months before study vaccination.
3. At least 8 weeks prior to enrollment, completed primary PCV regimen with PCV7, PCV10, or PCV13 with either a 2+1 or 3+1 regimen according to local recommendations; all doses of the primary regimen must be of the same vaccine.
 - a. 2+1: 2 priming doses followed by 1 booster dose administered prior to 2 years of age
or
 - b. 3+1: 3 priming doses followed by 1 booster dose administered prior to 2 years of age

4. Is PPSV23 vaccine-naïve (participant who has never received PPSV23), or PPSV23 vaccine-experienced (participant who has received not more than 1 dose of PPSV23) ≥ 5 years before study vaccination.

Demographics

5. Is an individual of any sex/gender, from ≥ 2 years to < 18 years of age, at the time of providing the informed consent/assent.

Assigned Female Sex at Birth

6. A participant assigned female sex at birth is eligible to participate if not pregnant or breastfeeding, and at least one of the following conditions applies:
 - Is not a POCBP
OR
 - Is a POCBP and:

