8 STUDY ASSESSMENTS AND PROCEDURES

- Study procedures and their timing are summarized in the SoA.
- Adherence to the study design requirements, including those specified in the SoA, is essential and required for study conduct.
- The investigator is responsible for ensuring that procedures are conducted by appropriately qualified (by education, training, and experience) staff. Delegation of study-site personnel responsibilities will be documented in the Investigator Trial File Binder (or equivalent).
- All study-related medical decisions must be made by an investigator who is a qualified physician.
- All screening evaluations must be completed and reviewed to confirm that potential participants meet all eligibility criteria. The investigator will maintain a screening log to record details of all participants screened and to confirm eligibility or record reasons for screening failure, as applicable.
- Procedures conducted as part of the participant's routine clinical management (eg, blood count) and obtained before providing documented informed consent/assent may be used for screening or baseline purposes provided the procedures meet the protocol-specified criteria and were performed within the time frame defined in the SoA.
- Additional evaluations/testing may be deemed necessary by the investigator and or the Sponsor for reasons related to participant safety. In some cases, such evaluation/testing may be potentially sensitive in nature (eg, HIV, hepatitis C), and thus local regulations may require that additional informed consent/assent be obtained from the participant (or participant's legally acceptable representative). In these cases, such evaluations/testing will be performed in accordance with those regulations.
- The maximum amount of blood collected from each participant over the duration of the study will not exceed the volume mentioned in Appendix 2.
- Repeat or unscheduled samples may be taken for safety reasons or for technical issues with the samples.

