10.2 Appendix 2: Clinical Laboratory Tests

- The tests detailed in [Table 7](#) will be performed by the local laboratory.
- Protocol-specific requirements for inclusion or exclusion of participants are detailed in Section 5 of the protocol.
- Additional tests may be performed at any time during the study as determined necessary by the investigator or required by local regulations.

Table 7 Protocol-required Safety Laboratory Assessments

Laboratory Assessments	Parameters
Pregnancy Testing	• Highly sensitive serum or urine hCG pregnancy test (as needed for POCBP)
hCG=human chorionic gonadotropin; POCBP=participant/participants of childbearing potential	

The investigator (or medically qualified designee) must document their review of each laboratory safety report.

Blood volumes collected from each participant over the duration of the study are detailed in [Table 8](#).

Country-specific criteria are included in Appendix 7.

Table 8 Blood Volumes Collected by Visit for Immunogenicity Assessments

	Visit 1	Visit 3	Total
Parameter	Approximate Blood Volume		
Immunogenicity assessment	10 mL	10 mL	20 mL
Note: The maximum blood volume to be collected for each visit in this population should follow local guidelines/recommendations, if specified.			

10.3 Appendix 3: Adverse Events: Definitions and Procedures for Recording, Evaluating, Follow-up, and Reporting

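### Do the two blood-draw limits in the EEA note to Table 8 contradict each other because their percentages imply different blood volumes per kg?

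*Combined protocol and SAP*

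**What the plan says.** Table 8 in Section 10.2 (Appendix 2) plans 10 mL of blood at Visit 1 and 10 mL at Visit 3, 20 mL in total, under the label "Approximate Blood Volume". Its footnote defers to local guidance on maximum volumes where such guidance exists.

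Section 10.7.2 (Appendix 7) then adds a stricter layer for one region: "For study sites in EEA countries, the following note applies to" Table 8. The note has two limits:

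- Single time point: "The blood draw limit should not exceed the EMA recommendation of 0.9 mL/kg body weight, which corresponds to 1% of total blood volume".
- Any 4-week period: "the blood draw limit should not exceed 2.4 mL/kg body weight, which is equivalent to 3% of the total blood volume".

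Neither percentage is marked as approximate, and no section of the protocol states a blood volume per kg of body weight.

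Three other places bear on the size of the matter. Enrolment starts at 2 years of age (Section 5.1, criterion 5). The two scheduled samples fall on Day 1 and at Visit 3, whose window is "Day 30 to Day 44" (Section 1.3). Section 8 also allows extra sampling: "Repeat or unscheduled samples may be taken for safety reasons or for technical issues with the samples".

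**The concern.** Two adjacent sentences convert mL/kg into a share of total blood volume, and the conversions do not use the same factor. One implies 90 mL/kg and the other 80 mL/kg, a ratio of 1.125. If 80 mL/kg were the right base, a draw at the first limit would be 1.125% of blood volume, above the 1% that the note gives for it.

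The note protects children, possibly as young as 2, so the inconsistency deserves a check. A site or ethics committee that worked from the percentage could arrive at a smaller permitted single draw than one that worked from mL/kg. In the smallest children that could decide whether the full 10 mL sample may be taken.

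**Working it through.** **Inputs.** The EEA note in Section 10.7.2 gives 0.9 mL/kg with 1%, and 2.4 mL/kg with 3%. Table 8 gives 10 mL per visit. Section 1.3 gives Day 1, and Day 30 to Day 44.

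**1. Exact reading.** Implied blood volume = limit ÷ stated fraction.

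- 0.9 / 0.01 = 90 mL/kg
- 2.4 / 0.03 = 80 mL/kg

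No single volume gives both equivalents exactly.

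**2. Could rounding of the mL/kg figures explain it?** With each limit rounded to one decimal and the percentages exact:

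- 0.85 / 0.01 to 0.95 / 0.01 = 85 to 95 mL/kg
- 2.35 / 0.03 to 2.45 / 0.03 = 78.3 to 81.7 mL/kg

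The ranges do not overlap, so this does not explain it.

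**3. Could rounding of the percentages explain it?** With the limits exact and the percentages rounded to whole numbers:

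- 1%: 0.9 / 0.015 to 0.9 / 0.005 = 60 to 180 mL/kg
- 3%: 2.4 / 0.035 to 2.4 / 0.025 = 68.6 to 96 mL/kg

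The ranges overlap from 68.6 to 96 mL/kg. Both candidate volumes lie inside:

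| Blood volume | 0.9 mL/kg is | 2.4 mL/kg is |
|---|---|---|
| 80 mL/kg | 1.125%, rounds to 1% | 3.0% |
| 90 mL/kg | 1.0% | 2.67%, rounds to 3% |

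**4. Do the mL/kg limits conflict?** They cover different time frames. Two draws at the single-draw limit total 2 × 0.9 = 1.8 mL/kg, below 2.4 mL/kg, so a site can satisfy both.

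**5. What would the stricter reading change?** Suppose a site took 1% of 80 mL/kg, that is 0.8 mL/kg. A 10 mL draw fits from 10 / 0.9 = 11.1 kg under the stated limit, and from 10 / 0.8 = 12.5 kg under this reading. For a child of weight w kg, the difference in permitted volume is min(10, 0.9w) − min(10, 0.8w):

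| Weight (kg) | Difference (mL) |
|---|---|
| 9 | 0.9 |
| 10 | 1.0 |
| 11.1 | 1.1 (largest) |
| 12 | 0.4 |
| 12.5 and above | 0 |

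**6. Does the 4-week limit come into play?** The scheduled draws are 30 − 1 = 29 to 44 − 1 = 43 days apart, always more than 28. If a repeat sample put two 10 mL draws inside 4 weeks, they would fit from 20 / 2.4 = 8.3 kg. If instead 90 mL/kg were the common base, 3% would be 2.7 mL/kg and the threshold 20 / 2.7 = 7.4 kg. So a common base could move either limit, in opposite directions.

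**The case for a change.** The best case for a change is that the note sets a safety limit and should not need interpretation. It states its equivalents flatly, while the table it qualifies does label its volumes as approximate. Rounding of the mL/kg figures cannot rescue it (step 2). Someone who checks the limit by percentage could reach a different answer for a child under 12.5 kg, and adding one word would cost almost nothing.

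Part of this stands: the two equivalents cannot both be exact, and the note does not say that they are rounded. The rest does not carry. The label in Table 8 describes draw volumes, so its absence from a percentage conversion says little about how precise that conversion is meant to be. The prohibition in each sentence attaches to the mL/kg figure, and the percentage follows in a descriptive clause, so the note already shows which number binds. To reach the stricter draw, a site would have to put aside that figure, infer a blood volume from a sentence about a different time frame, and apply 1% to it. Nothing in the protocol tells it to.

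Putting both limits on one stated volume would mean choosing that volume. The documents do not give one, and the cited European recommendation is not among them.

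**Conclusion.** No change to the plan follows. The arithmetic behind the concern is right: 90 against 80 mL/kg if the percentages are exact. But it does not show that any figure is wrong, because one-digit percentages are compatible with both limits anywhere from 68.6 to 96 mL/kg. A site that follows the note as written has one definite limit per draw and one per 4 weeks, and the two do not conflict.

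The practical effect is nil under that reading. Under the stricter reading it is at most about 1.1 mL per draw, confined to children under 12.5 kg at EEA sites. Whether any such children enrol is an assumption, since the protocol gives no weights. Immunogenicity and safety endpoints, analysis populations, sample size and power do not depend on it.

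The conclusion rests on two readings: that 1% and 3% are whole-number descriptions, and that the mL/kg figures are the binding ones. The sentence structure supports the second; the first is the ordinary way to read such figures but is not stated. Marking the percentages as approximate would be a harmless clerical tidy-up with no gain for participants or results. This review takes no view on which limit or blood volume is correct.

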10.8 Appendix 8: Abbreviations

Abbreviation	Expanded Term
ACIP	Advisory Committee on Immunization Practices
AE	Adverse event
APaT	All-Participants-as-Treated
CFR	Code of Federal Regulations
CHMP	Committee for Medicinal Products for Human Use
CI	Confidence interval
cLDA	Constrained longitudinal data analysis
CONSORT	Consolidated Standards of Reporting Trials
CRF	Case report form
CSR	Clinical study report
CTFG	Clinical Trial Facilitation Group
deOAc	De-O-acetylated
DMC	Data Monitoring Committee
DNA	Deoxyribonucleic acid
ECG	Electrocardiogram
ECI	Event of clinical interest
ECL	Electrochemiluminescence
eCRF	Electronic case report form
EDC	Electronic data collection
EEA	European Economic Area
ELISA	Enzyme-linked immunosorbent assay
EMA	European Medicines Agency
EOC	Executive Oversight Committee
EU	European Union
eVRC	Electronic vaccination report card
FAS	Full Analysis Set
FBR	Future biomedical research
FDA	Food and Drug Administration
FDAAA	Food and Drug Administration Amendments Act

Abbreviation	Expanded Term
FSH	Follicle-stimulating hormone
FSR	First site ready
GCP	Good Clinical Practice
GMC	Geometric mean concentration
GMFR	Geometric mean fold rise
GMT	Geometric mean titer
hCG	Human chorionic gonadotropin
HIV	Human immunodeficiency virus
HRT	Hormone-replacement therapy
IA	Interim analysis(es)
IB	Investigator's Brochure
ICF	Informed Consent/Assent Form
ICH	International Council for Harmonisation of Technical Requirements for Pharmaceuticals for Human Use
ICMJE	International Committee of Medical Journal Editors
ID	Identification
IEC	Independent Ethics Committee
IgG	Immunoglobulin G
IM	Intramuscular(ly)
IMP	Investigational Medicinal Product
IND	Investigational New Drug
IPD	Invasive pneumococcal disease
IRB	Institutional Review Board
IRT	Interactive response technology
IUD	Intrauterine device
IUS	Intrauterine hormone-releasing system
LAM	Lactational amenorrhea method
M&N	Miettinen and Nurminen
MOPA	Multiplexed Opsonophagocytic Assay
mRNA	Messenger RNA
NIP	National immunization program

Abbreviation	Expanded Term
OPA	Opsonophagocytic activity
PCV	Pneumococcal conjugate vaccine
Pn ECL	Pneumococcal electrochemiluminescence
PnPs	Pneumococcal polysaccharide
POCBP	Participant/participants of childbearing potential
PP	Per-protocol
PPSV23	Pneumococcal vaccine, polyvalent (23-valent) (PNEUMOVAX™23) (Serotypes 1, 2, 3, 4, 5, 6B, 7F, 8, 9N, 9V, 10A, 11A, 12F, 14, 15B, 17F, 18C, 19F, 19A, 20, 22F, 23F, and 33F)
PQC	Product quality complaint
RNA	Ribonucleic acid
SAC	Scientific Advisory Committee
SAE	Serious adverse event
SAP	Statistical analysis plan
SARS-CoV-2	Severe acute respiratory syndrome coronavirus 2
SLAB	Supplemental laboratory test(s)
SoA	Schedule of activities
SOC	System organ class
SUSAR	Suspected unexpected serious adverse reaction
US	United States
V116	Pneumococcal 21-valent conjugate vaccine
VRC	Vaccination report card
WHO	World Health Organization

